5. STUDY TREATMENT AND DURATION

There will be no dispensing of any study medication or protocol-specified procedures associated with participation in this registry. All medical treatment, including medications, is solely at the discretion of the treating physician in accordance with their usual care.

The total duration of the registry is approximately 9 years, including approximately 4 to 5 years for patient enrolment and 4 to 5 additional years for follow-up on all enrolled patients. Dermatologists will enrol eligible patients who are current users of etanercept at any time after they initiate such treatment for plaque psoriasis. The Sponsor expects to enrol the first patient in Q4 2010, with all follow-up to be completed in 2018. Follow-up will occur every 3 months during the first 2 years of the study and every 6 months thereafter (year 3 through the end of participation). Each patient is expected to participate for 5 years, or until the registry is completed in 2018, whichever comes first.

6. STUDY PROCEDURES

6.1. Schedule of Assessments

For the purpose of routine clinical care of chronic psoriasis, it is anticipated that follow-up with the treating physician will occur at least once every 3 months for the first two years after receiving the first dose of etanercept at which time RPs will collect follow up data.

Alternatively, the patient and the parent/legal representative may be contacted by phone. Thereafter, data collection will take place every 6 months (also in conjunction with routine clinical visits) from year 3 through the end of follow-up, as shown in the registry flowchart. The registry will allow a window of ± 4 weeks around the date of the scheduled data collection. Infections, malignancies, SAEs, etanercept discontinuations and registry discontinuations may be reported at any time during follow-up.

At each scheduled data collection point, the RP will record information on the registry outcomes of interest, comorbid medical conditions, medication use, and SAEs. In order to maximise retention and capture relevant data, a highly structured approach to managing follow-up is planned. Centralised registry resources will proactively contact sites (quarterly during the first 2 years, semi-annually thereafter) in advance of scheduled data collection times to remind the RP to collect and report study data. At that time, registry staff will update contact information regarding the patients and their physicians. If data has not been received within the expected timeframe, CRO will contact sites several times following the original due date. They will make every reasonable effort (including direct-to-patient calls) to obtain this data before considering a patient lost to follow-up. For each site, the electronic data capture (EDC) system will also provide active, up-to-date workflow reports alerting them to upcoming and overdue timepoints.

If, during the study period, the enrolled site is not actively following the patient, CRO will provide the enrolled site with the contact information for the patient's primary health care provider (or other treating physician) and a standard form letter (with a paper copy of the questionnaire) that the site can fax/mail to the physician requesting the follow-up information on behalf of the registry. The patient's treating physician will be asked to complete the questionnaires and return them to CRO for data entry.

6.2. Data Collection

Data collection is designed to minimise the burden on the participating RPs and patients, and maximise retention. Electronic case report form for data entry, are designed to elicit the specific desired data points.

Data will be collected from the following sources:

- Prospective data provided by the treating physicians (this may be multiple physicians including the prescribing dermatologist or RP, and other physicians responsible for the patient's care over the course of the study);
- Prospective data collected from patient interviews during the less frequent follow-up phase of the study.
- Retrospective data collected by medical record abstraction

The RP will provide information on current prescriptions and status of each registry patient at enrolment and at each scheduled follow-up assessment. Following enrolment in the registry, the RP will also provide information by retrieving medical record information at his/her own institution and other health care settings, as appropriate. Some patients may be undergoing active treatment with etanercept at the time of registry enrolment, and the lag between initiating etanercept treatment and active data collection as part of the registry will necessitate the abstraction of relevant safety-related and treatment pattern information from the medical record. The number of patients meeting this criterion is expected to be limited.

6.2.1. Baseline Visit

During the enrolment visit, the site will be instructed to obtain additional information regarding the patient, including secondary contact information and contact information for the patient's primary health care provider.

The following information will be collected:

1. Date of informed consent(s)/assent
2. Patient/legal representative contact information, including secondary contacts and primary health care provider details, if different than RP
3. Demography [age, gender, weight, race/ethnicity (where allowed by local regulation)]
4. Medical history/co-morbid medical conditions
5. Plaque psoriasis history
 - a. Physician's global subjective assessment of disease severity (four-point scale)
 - b. Prior treatments or therapies, including topical agents and immunosuppressive therapies and the patient's response to each.
6. Etanercept Treatment
 - a. Initial prescribed etanercept treatment regimen
 - b. Date of first dose
7. Concomitant medications, including immunosuppressants
8. Retrospective medical record abstraction for patients with historical treatment with etanercept will also include:
 - a. Etanercept dosing history
 - b. Use of additional systemic therapies since starting etanercept
 - c. Occurrence of serious and/or pre-specified opportunistic infections and SAEs

Note: Due to the significance of the AEs of interest (serious and opportunistic infections and malignancies), it is considered highly likely that these events, if they occurred, would be documented in the medical record of the prescribing RP. Retrospective data for other SAEs overall, however, may not be consistently recorded; therefore, all retrospective SAEs will be collected but analysed separately.

6.2.2. Follow-up Visit

FOLLOW-UP: YEAR 1 THROUGH 2

Regardless of the duration of etanercept exposure at the time of registry enrolment, all patients will be followed prospectively using the same schedule. During follow-up, the RP or other trained site staff will collect data during routine clinical visits. Routine clinical visits may not coincide with registry timepoints; therefore alternatively, the RP, trained site staff or CRO registry staff may administer follow-up questionnaires via phone interviews.

The following data will be collected every 3 months (\pm 4 weeks) during the first 2 years of participation:

1. Updated informed consent information (e.g., if patient turns 18 since last follow-up)
2. Updated contact information
3. Status of etanercept exposure (ongoing/completed/discontinued/reason for discontinuation)
4. Requirement for additional psoriasis treatment
 - a. Continued etanercept
 - b. Other systemic treatments
 - c. Use of topical agents
 - d. Reason for treatment decision
5. Physician's global subjective assessment of plaque psoriasis severity
6. Changes in medical status, including new onset comorbid medical conditions
7. Changes/additions to concomitant medications
8. AEs as described in [Section 2.1.1](#), Safety Endpoints
 - a. Serious and pre-specified opportunistic infections
 - b. Malignancies
 - c. Other AEs

FOLLOW-UP: YEAR 3 THROUGH YEAR 5/END OF FOLLOW-UP

The following data will be collected every 6 months (\pm 4 weeks) during year 3 through the end of participation:

1. Updated informed consent information (e.g., if patient turns 18 since last follow-up)

2. Updated contact information
3. Status of etanercept exposure (ongoing/completed/discontinued/reason for discontinuation)
4. Requirement for additional psoriasis treatment
 - a. Continued etanercept
 - b. Other systemic treatments
 - c. Use of topical agents
 - d. Reason for treatment decision
5. Physician's global subjective assessment of plaque psoriasis severity
6. Changes in medical status, including new onset comorbid medical conditions
7. Changes/additions to concomitant medications
8. AEs as described in [Section 2.1.1](#), Safety Endpoints
 - a. Serious or pre-specified opportunistic infections
 - b. Malignancies
 - c. Other AEs

6.2.3. Patient Withdrawal

Patients may withdraw from the study at any time at their own request, or they may be withdrawn at any time at the discretion of the investigator or sponsor for safety, behavioural, or administrative reasons. Patients and/or their respective parents/legal representatives if minors have the right to withdraw from the registry at any time, without prejudice, and are not obligated to state their reasons for registry discontinuation. If a patient or parent/legal representative declares his or her wish to discontinue from the registry, the RP will complete a discontinuation CRF. All reasonable efforts will be made to establish whether the reason for discontinuation was related to a registry outcome of interest or other adverse event. The Sponsor reserves the right to suspend or terminate the registry or part of the registry at any time for any reason.

Before considering a patient lost to follow-up, the RP/site staff will make all reasonable attempts to contact the patient or the parent/legal representative to ensure that a registry outcome of interest is not the underlying reason for the inability to contact the patient. For each missed scheduled encounter with the RP, several attempts to reach the patient by phone, e-mail and post will be made with a minimum of three attempts and a period of approximately one week between attempts. If no response is received within a month of the follow-up timepoint, CRO registry staff will contact any other known healthcare providers to determine if the reason for failure to respond is health-related, and to determine the health status of the patient. If CRO is unable to obtain the follow-up data from the RP or other provider(s), they will contact the secondary patient contact to obtain vital status. The informed consent process and forms will describe these procedures, including the possibility

of contacting the patient's non-RP health care providers. Data collected prior to loss to follow-up will be included in all analyses.

If the patient withdraws from the study, and also withdraws consent for disclosure of future information, no further evaluations should be performed, and no additional data should be collected. The sponsor may retain and continue to use any data collected before such withdrawal of consent.

7. DATA ANALYSIS/STATISTICAL METHODS

The purpose of the registry is to assess the long-term safety of etanercept in paediatric patients with plaque psoriasis and to infer effectiveness by describing the pattern of treatment of psoriasis in this population.

7.1. General considerations

All AE verbatim terms will be recorded and coded using MedDRA. Statistical analysis of all data will be performed using SAS[®] statistical software (SAS Institute, Cary, NC, USA).

Frequencies of defined outcomes will be described. If possible, analyses will also be performed using the different etanercept treatment status (i.e., current/recent versus past treatment) and etanercept cumulative dose exposure groups.

Analysis of the characteristics of patients enrolled in the registry and of those who did not consent to participate (to the extent feasible) will help evaluate whether there are any differences between registry enrollees and non-respondents, i.e., generalizability.

Primary analyses will be limited to prospective data, i.e., events reported during participation in the registry. Serious and pre-specified opportunistic infections and malignancies reported as part of retrospective data collection will be summarized separately.

7.2. Sample Size Calculation

No formal sample size calculation will be used to manage enrolment in the study since the goal is to obtain participation by all eligible patients. Current available data are insufficient to project population based estimates of paediatric patients with severe psoriasis treated with conventional systemic therapy who are not well-controlled and may warrant further intervention such as that potentially afforded by etanercept.

7.3. Baseline Assessment

The demographic and clinical profile of the registry population will be described using baseline data. Patient demographics, psoriasis severity, history of psoriasis and psoriasis treatment(s) prior to first etanercept administration will be summarized. Data will be

summarized overall and by status at enrolment to explore whether the patients treated prior to registry enrolment are different than the overall population.

Continuous variables (e.g., age) will be reported as means and standard deviations. Categorical variables (e.g., gender) will be summarized as number and percentage (%) of the total registry population.

7.4. Primary Analyses

It is anticipated that the etanercept treatment status for each patient will change throughout follow-up. A standard course of etanercept treatment is expected to last 24 weeks. Patients successfully responding to the first etanercept treatment course may be exposed to subsequent treatment (i.e., when patients experience a flare) and the time window between two (or more) consecutive courses of treatment may vary substantially.

Patterns of treatment with etanercept will be described (to the extent possible) as follows:

- Frequency of premature discontinuation of etanercept (i.e., treatment course < 24 weeks)
- Frequency of subsequent treatment with systemic therapies (including re-treatment with etanercept)
- Intervals between etanercept treatment and subsequent course of systemic therapy (including etanercept)
- Means and percentages of demographic and disease characteristics of patients who experience and those who do not experience discontinuation of etanercept
- Frequency of discontinuation stratified by cumulative dose, duration of use, and other etanercept use patterns.

Serious and Pre-specified Opportunistic Infections

Time at risk of serious and pre-specified opportunistic infections will correspond to current/recent treatment with etanercept. Current/recent etanercept treatment will be defined as time between the dates of first and last dose within a treatment course plus 28 days. Risk will be estimated as number of events over cumulative time at risk. Estimates of relative risk of these infections will be used to quantify any association between the study outcomes and current/recent treatment with etanercept. In order to calculate relative risk, incidence of infection during cumulative current/recent treatment with etanercept will be compared to incidence of infection during cumulative period without use of etanercept.

Should any patient develop tuberculosis (TB) during the course of follow-up, the Sponsor will conduct standardised incidence ratio (SIR) analyses using geographically appropriate population based rates of TB applied to time at risk on etanercept.

Analyses may include more than one episode of infection experienced by a single individual. Stratified analyses of the events of interest by etanercept dose, duration of treatment, and

number of treatment course (i.e., first, second, etc.) will be attempted, depending on the number of events reported.

Malignancies

Time at risk of incident malignancies will be defined as time since the date of first dose of etanercept treatment to the date of malignancy diagnosis or end of follow-up if no malignancy has been diagnosed. Long-term risk of incident malignancy in patients who have ever received etanercept will be estimated as number of events over the total time at risk. Should any patient develop cancer during follow-up, the Sponsor will calculate SIRs for malignancy (age and gender-adjusted) using geographically appropriate population-based norms. Although all malignancies reported throughout the study will be described, only the first diagnosis of malignancy occurring during the follow-up will be considered in the SIR analysis.

Other SAEs

Time at risk of all other SAEs will correspond to current/recent treatment with etanercept. Current/recent etanercept treatment will be defined as time between the dates of first and last dose within a treatment course plus 28 days.

A descriptive analysis of SAEs will be conducted. Any grouping and stratification will be dependent on the number and type of events reported.

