11.4. Final Analyses and Reporting

A final registry report will be prepared at closure of the registry database, when all data collection procedures are completed. The final report will encompass all planned analyses, including a description of the complete registry population and estimates of events rates, as described above and in the SAP.

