### **5.3 Definition and measurement of exposure/risk windows**

#### **5.3.1 Etanercept**

##### **TREATMENT PERIODS (INITIAL AND SUBSEQUENT)**

It is anticipated that the etanercept treatment status for each patient will change throughout follow-up. A standard course of etanercept treatment is expected to last up to 24 weeks. Patients successfully responding to the first etanercept treatment course may be exposed to subsequent treatment (i.e., when patients experience a disease flare) and time window between 2 (or more) consecutive courses of treatment may vary substantially.

For the initial course of etanercept, whether the patient completed 24 weeks of treatment is recorded (yes/no), and if no, the number of weeks of treatment will be reported. Completion of initial 24 weeks of etanercept is defined as starting the first dose of etanercept within 30 day before the enrolment date or any time after enrolment date, and continuing for at least 168 days.

For each subsequent treatment period of etanercept, start and stop dates of treatment are collected. For all subsequent periods, the duration of treatment in weeks will be calculated. Cumulative exposure will be calculated by the sum, for each etanercept treatment period, of: [last dose date – first dose date] + 28. If there are less than 28 days between treatment periods, exposure will be considered uninterrupted (i.e., part of the same treatment period).

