#### **6.6 Derivations**

The following derived/calculated values will be used:

[figure not shown]
- Age at enrollment in years:  $[\text{date of enrollment} - \text{date of birth} + 1] / 365.25$
- Duration of disease at enrollment in years:  $[\text{date of enrollment} - \text{date of diagnosis} + 1] / 365.25$
- Cumulative exposure in weeks by the duration of chronic exposure for each period of etanercept exposure:  $[(\text{last dose date} - \text{first dose date} + 1) + 28] / 7$ . A treatment period is defined as continuous treatment with no interruptions of more than 28 days. Restarting treatment within 28 days is considered as having continuous exposure
- Duration of each etanercept treatment period (in weeks):  $(\text{last dose date} - \text{first dose date} + 1) / 7$
- Time at risk of malignancy (in years):  $[\text{date of malignancy diagnosis or end of follow-up if no malignancy is found} - \text{initial treatment dose date} + 1] / 365.25$

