## PURPOSE SAP

### Protocol # B1801035

- Summary of patients requiring additional treatment with systemic therapy (etanercept or other non-etanercept therapies)
  - Proportion of patients requiring additional treatment, by subsequent treatment type
- Summary of overall treatment over the entire 5 years of study participation starting from enrollment to the end of follow-up.
  - Duration of exposure to etanercept
  - Cumulative dose of etanercept
  - Total number of treatment periods of etanercept [complete ( $\geq 24$  weeks), incomplete ( $< 24$  weeks) and overall]

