## **8. Other Analyses**

Additional exploratory analyses may be performed, depending on the availability of data, including replication of certain analyses stratified by level of cumulative exposure.

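### Stratifying discontinuation by final cumulative dose and duration of use lets the act of stopping help set the strata, so the table can show an association where none exists

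*Protocol*

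**What the plan says.** Among the treatment-pattern descriptions under Primary Analyses, Protocol 7.4 lists "Frequency of discontinuation stratified by cumulative dose, duration of use, and other etanercept use patterns". An earlier item in the same list is "Frequency of premature discontinuation of etanercept (i.e., treatment course < 24 weeks"; the stratified item itself says only discontinuation, without the word premature. The whole list is to be produced as far as possible.

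The SAP builds both stratifiers from dose dates:
- Section 6.6 takes the duration of a treatment period as (last dose date − first dose date + 1)/7 weeks.
- Section 5.3.1 says "Cumulative exposure will be calculated by the sum, for each etanercept treatment period", from the same two dates plus 28 days.
- Section 7.2 reports cumulative dose within a "Summary of overall treatment over the entire 5 years of study participation starting from enrollment to the end of follow-up".

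Neither document fixes exposure at course start, sets a landmark or uses time-updated exposure for discontinuation, and neither plans a time-to-event method for it.

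SAP 7.7 reports discontinuation before and after 24 weeks by reason, and does not carry the stratified item. SAP 8 allows, as optional exploratory work, "replication of certain analyses stratified by level of cumulative exposure". Protocol 11.4 says "The final report will encompass all planned analyses", and points both to the protocol's own description and to the SAP.

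**The concern.** Final duration and final cumulative dose are consequences of when the patient stops. Sorting patients by them and then counting who stopped conditions partly on the outcome.

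Protocol 2.1.2 and SAP 7.7 make discontinuation for lack of effect the registry's proxy for effectiveness. A table with less discontinuation at higher cumulative dose could therefore be misread as a dose-response, or as better tolerance at higher exposure, when the sorting alone can produce it. Protocol 11 provides for public dissemination of the results and for reporting to the EMA.

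**Working it through.** The documents give no expected discontinuation rate and no figure for this table, so there is nothing to reproduce. The check asks what the table would show if dose and duration had no effect on stopping.

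**Inputs from the documents.** Courses of 24 weeks as standard (Protocol 7.4); continuous use beyond 24 weeks possible (SAP 5.2.5); follow-up as in Protocol 5: "Each patient is expected to participate for 5 years, or until the registry is completed in 2018, whichever comes first".

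**Assumptions.** Constant stopping hazard with median m = 26, 52, 104 or 208 weeks; follow-up uniform on 4–5 or 1–5 years. Weekly dose is independent of stopping, generated from the 0.8 mg/kg of the background trial with body weight of mean 50 kg and SD 15 and a 50 mg cap. One course per patient in steps 2 to 4; 400,000 simulated patients per scenario.

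**1. Premature discontinuation by course duration.** The outcome is duration < 24 weeks. Split at 24 weeks, the table reads 100% and 0%. This needs no assumption.

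**2. Premature discontinuation by tertile of cumulative dose, one course.** The share stopping before 24 weeks is p = 1 − 2^(−24/m). With equal weekly doses all early stoppers sit at the bottom, so the lowest tertile shows min(1, p ÷ 1/3).

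| m (weeks) | p | Lowest tertile, equal doses | Simulated tertiles, varying doses |
|---|---|---|---|
| 26 | 47.3% | 100% (middle: (47.3 − 33.3)/33.3 = 42%) | 98.3/43.8/0.0% |
| 52 | 27.4% | 82% | 81.0/1.4/0.0% |
| 104 | 14.8% | 44% | 44.2/0.0/0.0% |
| 208 | 7.7% | 23% | 23.2/0.0/0.0% |

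**3. Any discontinuation by tertile of cumulative dose, one course.** Observed duration is the smaller of stopping time and follow-up; cumulative dose is weekly dose × observed duration.

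| m (weeks) | Follow-up 4–5 years | Follow-up 1–5 years |
|---|---|---|
| 26 | 100/100/99.4% | 100/99.2/87.3% |
| 52 | 100/100/86.3% | 99.6/86.2/63.3% |
| 104 | 100/92.6/43.8% | 91.7/55.9/37.7% |
| 208 | 95.2/52.6/14.4% | 67.6/31.8/18.4% |

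A separate run at 104 weeks and 1–5 years gave about 93/55/37%. The false gradient needs patients still on treatment at the end of follow-up. Where almost everyone stops (26 weeks, 4–5 years) it nearly disappears.

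**4. Which stratifiers are flat under the same null (m = 104 weeks).**
- Starting weekly dose: 78.7/78.9/78.8% (4–5 years) and 61.7/61.8/61.8% (1–5 years).
- Time-updated cumulative-dose bands with person-time (4–5 years): 0.347/0.347/0.346 per person-year, against a true rate of (ln 2/104) × (365.25/7) = 0.348.
- Person-time within tertiles of *final* cumulative dose does not cure it: 1.686/0.422/0.109 per person-year.

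**5. Repeated courses.** Assume 30% of courses stop early and the others last 24 weeks, with mean gaps of 12 to 104 weeks, 4–5 years of follow-up, and weekly dose independent of stopping. Premature stopping per course by cumulative-dose tertile ran from 29.8/28.4/27.5% to 38.5/29.9/23.6%. A second set of repeat-course runs gave about 33/31/28% to 44/30/25%. Counted per patient (ever stopped early), the pattern was mostly flat or reversed, for example 59/76/85% at a 52-week mean gap that varied between patients, because more courses mean both more dose and more chances to stop early.

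**The case against.** The case against has several parts that stand.

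- **Outcome.** A reader might infer that the 100%/0% split describes the whole item. It does not: the item says discontinuation, and the split holds only if premature discontinuation is meant and the stratifier is course duration.
- **Magnitude.** A reader might also infer a table of about 90/0/0% by cumulative-dose tertile (30% early stopping ÷ one third of patients = 90%). That needs one course per patient and an early-stopping rate the documents do not give. They expect repeat courses, and step 5 then gives a modest gradient or a reversed one. No general claim about direction is supported.
- **Effectiveness.** Treatment patterns are not the only route to effectiveness. SAP 4, 5.2.5 and 7.7 add change in psoriasis severity from baseline.
- **SAP coverage.** SAP 7.7 omits the item, and Section 8 is optional and does not name discontinuation. Protocol 7.1 mentions cumulative-dose groups for outcomes generally, so Section 8 may be meant for safety rates. It does not show that the stratification survives. SAP 9.3 also defines the final report by the SAP's analyses alone.
- **Purpose.** SAP 6.2 calls the study descriptive and non-comparative, SAP 7 plans no hypothesis test, and the documents themselves propose no dose-response reading.

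What does not stand is that this settles the matter. The SAP is silent on the protocol item and does not withdraw it, and Protocol 11.4 still ties the final report to the protocol's own description. Calling the table descriptive does not help when its strata are partly set by the event being counted.

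**Conclusion.** The item is wrong as written, but the defect is limited to one descriptive table and its consequence is low to moderate. What is certain is the mechanism: both stratifiers accrue up to the stop date. The 100%/0% split for premature discontinuation by course duration is also certain.

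Everything else depends on the assumed stopping rates, follow-up and course patterns. With single courses and some patients still on treatment, the false gradient can be strong (91.7/55.9/37.7% at a 104-week median and 1–5 years). It is nearly flat if almost everyone stops. With repeated courses it is modest per course and mostly flat or reversed per patient. Other use patterns named in the item, such as course number, are not affected if they are fixed at course start. The SAP's summaries before and after 24 weeks use duration to define the outcome, not to stratify it, and do not share the fault.

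**What to change.** State in the SAP that the protocol's stratification by final cumulative dose and duration of use is replaced as follows:

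- Describe time to discontinuation from the start of each course, as cumulative incidence by reason, censoring patients still on treatment.
- Stratify only by features known at course start (starting regimen, course number, age, baseline severity, prior systemic therapy), or by time-updated exposure with person-time denominators.
- Report duration and cumulative dose as outcomes, as SAP 7.2 already does.
- Exclude discontinuation from the cumulative-exposure replications in SAP 8.

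Patients already on etanercept at enrolment should enter the risk set at enrolment, or be shown separately using the enrolment type in SAP 6.5.

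The cost is SAP wording and one replaced output. The first-dose date (Protocol 6.2.1), discontinuation status and reason (Protocol 6.2.2), and start and stop dates of later periods (SAP 5.3.1) are already collected.
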